9 STUDY ASSESSMENTS AND PROCEDURES

- Study procedures and timing are summarized in the Schedule of Activities.
- Protocol waivers or exemptions are not allowed.
- All immediate safety concerns must be discussed with the Sponsor immediately upon occurrence or awareness to determine if the participant should continue or discontinue treatment.

- Adherence to the study design requirements, including those specified in the Schedule of Activities, is essential and required for study conduct.
- All screening evaluations must be completed and reviewed to confirm that potential participants meet all eligibility criteria before randomization. The investigator will maintain a screening log to record details of all participants screened and to confirm eligibility or record reasons for screening failure, as applicable.
- Procedures conducted as part of the participant's routine clinical management (eg, blood count) and obtained before signing of informed consent may be utilized for screening or baseline purposes provided the procedure meets the protocol-defined criteria and has been performed within the timeframe defined in the Schedule of Activities.

9.1 Efficacy Assessments

9.1.1 Primary and Secondary Objectives

9.1.1.1 Prevention of Disease Progression

The primary objective will be to determine the impact of therapy on prevention of disease progression as defined below using a composite endpoint. This endpoint will be reached if the participant ever requires use of invasive mechanical ventilation or experience death.

Invasive mechanical ventilation is defined as the delivery of positive pressure to the lungs via an endotracheal tube (or tracheostomy).

9.1.1.2 Improvement in Clinical Status

The WHO has recommended clinical study for COVID-19 use a composite clinical endpoint and recommend use of an ordinal scale that measures participant's clinical status.⁴⁸ Ordinal data is a kind of categorical data with a set order or scale to it. Ordinal scales have been adopted in some current prospective clinical studies.⁴⁹ The following 8-point scale was proposed for the National Institute of Allergy and Infectious Diseases (NIAID) Adaptive COVID-19 Treatment Trial (ACTT) (ClinicalTrials.gov Identifier: NCT04280705). It will be used in this study.

- 1) Death
- 2) Hospitalized, on invasive mechanical ventilation or extracorporeal membrane oxygenation (ECMO)
- 3) Hospitalized, on non-invasive mechanical ventilation or high-flow oxygen devices
- 4) Hospitalized, requiring supplemental oxygen
- 5) Hospitalized, not requiring supplemental oxygen - requiring ongoing medical care (COVID-19 related or otherwise)
- 6) Hospitalized, not requiring supplemental oxygen - no longer requires ongoing medical care
- 7) Not hospitalized, limitation on activities and/or requiring home oxygen
- 8) Not hospitalized, no limitation on activities

Patients may change between states in this scale multiple times during any 24-hour period. The study team will record in the study record only the worst (ie, lowest) state for each day (midnight to midnight). The determination of the worst state to be recorded should be made as soon as possible after the completion of the day to be assessed.

ICU admission is defined as transfer of care within the hospital to a specialized medical care unit distinct from routine or intermediate (ie, stepdown) care. Given the increased demand for ICU beds as a consequence of the COVID-19 pandemic, all forms of ICUs (eg, surgical) and non-ICU beds have been converted into ICU care beds. Progression into any of these will be considered to meet these criteria.

Other elements of each point have been defined with the exception of ECMO (extra-corporeal membrane oxygenation). This scale captures similar information to the primary endpoint but has the advantage of capturing improvement. The “limitations of activities” in state #6 includes need for home oxygen therapy. Based on inclusion criteria, all study subjects will be in category 3 or 4, and can be extracted from the clinical record.

9.1.1.3 Improvement in Mortality

Mortality for this endpoint will be based on all-cause mortality at Day 28 which represent participants who are in state 1 of the Ordinal 8-point Outcome Scale.

For participants deaths, data will be collected on whether the death occurred after withdrawal of care and, if so, the reason for withdrawal of care will be recorded (eg, brain death, patient/family request, resource constraint).

9.1.1.4 Absence of Critical Disease

This endpoint is related to the primary endpoint. It is defined as the proportion of participants alive and free of respiratory failure on Day 28. Respiratory failure is defined by the type of resources required as defined by the use of any of these: mechanical ventilation, ECMO or oxygen delivery by noninvasive positive pressure or high-flow nasal cannula. Participants in state 4-8 of the Ordinal 8-point Outcome Scale meet this definition.

[figure not shown]
9.1.1.5 Recovery of Pulmonary Function

[figure not shown]
All participants randomized will be oxygen dependent and dependence on oxygen has been noted to be prolonged even after hospital discharge. We will assess recovery of pulmonary function by determining the proportion of patients returning to room air by Day 28. Participants in state 5, 6 and 8 of the Ordinal 8-point Outcome Scale meet this definition. Some participants in state 7 will.

9.1.1.6 Shortened Hospitalization

This endpoint will be defined as the proportion of participants alive and discharged home by Day 28. Home as a location will include any new facility that provides ongoing support short of full medical care such as a rehabilitation facility or assisted living facility. Participants in state 7-8 of the Ordinal 8-point Outcome Scale meet this definition.

Length of hospitalization will be defined as the number of days from the day of randomization to the date of discharge or Day 28, whichever is sooner, measured in days.

9.2 Adverse Events

The definitions of an AE or serious adverse event (SAE) can be found in [Appendix 3](#).

AEs will be reported by the participant (or, when appropriate, by a caregiver, surrogate, or the participant's legally authorized representative).

The investigator and any designees are responsible for detecting, documenting, and reporting events that meet the definition of an AE or SAE and remain responsible for following up AEs that are serious, considered related to the study treatment or the study, or that caused the participant to discontinue before completing the study.

Contacts for SAE reporting specified in [Appendix 3](#)

9.2.1 Time Period and Frequency for Collecting AE and SAE Information

Sections 5.5.1 in the Investigator's Brochure (IB) represent the Reference Safety Information to determine expectedness of serious adverse events for expedited reporting.

Following the subject's written consent to participate in the study, all SAEs, whether related or not related to study drug, must be collected, including those thought to be associated with protocol-specified procedures. All SAEs must be collected that occur during the screening period through 60 days after discontinuation of dosing.

9.2.2 Method of Detecting AEs and SAEs

Adverse events can be spontaneously reported or elicited during open-ended questioning, examination, or evaluation of a subject. (In order to prevent reporting bias, participants should not be questioned regarding the specific occurrence of one or more AEs.)

9.2.3 Follow-up of AEs and SAEs

- Nonserious AEs should be followed to resolution or stabilization, or reported as SAEs if they become serious (see Section [Appendix 3](#)).
- Follow-up is also required for nonserious AEs that cause interruption or discontinuation of study treatment and for those present at the end of study treatment as appropriate.
- All identified nonserious AEs must be recorded and described on the nonserious AE page of the CRF (paper or electronic). Completion of supplemental CRFs may be requested for AEs and/or laboratory abnormalities that are reported/identified during the course of the study.

All SAEs will be followed until resolution, until the condition stabilizes, until the event is otherwise explained, or until the participant is lost to follow-up (as defined in [Section 8.3](#)).

Further information on follow-up procedures is given in [Appendix 3](#).

9.2.4 Regulatory Reporting Requirements for SAEs

- Prompt notification by the investigator to the Sponsor of SAEs is essential so that legal obligations and ethical responsibilities towards the safety of participants and the safety of a product under clinical investigation are met.
- An investigator who receives an investigator safety report describing SAEs or other specific safety information (eg, summary or listing of SAEs) from the Sponsor will file it along with the Investigator's Brochure and will notify the IRB/IEC, if appropriate according to local requirements.

Sponsor or designee will be reporting adverse events to regulatory authorities and ethics committees according to local applicable laws including European Directive 2001/20/EC and FDA Code of Federal Regulations 21 CFR Parts 312 and 320. A SUSAR (Suspected, Unexpected Serious Adverse Reaction) is a subset of SAEs and will be reported to the appropriate regulatory authorities and investigators following local and global guidelines and requirements.

9.2.5 Pregnancy

If, following initiation of the study treatment, it is subsequently discovered that a participant is pregnant or may have been pregnant at the time of study exposure, including during at least 70 days after study product administration, the investigator must immediately notify the BMS Medical Monitor/designee of this event and complete and forward a Pregnancy Surveillance Form to BMS Designee within 24 hours of awareness of the event and in accordance with SAE reporting procedures described in [Appendix 3](#).

If the investigator determines a possible favorable benefit/risk ratio that warrants continuation of study treatment, or re-initiation of study treatment, a discussion between the investigator and the BMS Medical Monitor/designee must occur.

Follow-up information regarding the course of the pregnancy, including perinatal and neonatal outcome and, where applicable, offspring information must be reported on the Pregnancy Surveillance Form.

Any pregnancy that occurs in a female partner of a male study participant should be reported to Sponsor or designee. In order for Sponsor or designee to collect any pregnancy surveillance information from the female partner, the female partner must sign an informed consent form for disclosure of this information. Information on this pregnancy will be collected on the Pregnancy Surveillance Form.

If any sexual activity (eg, vaginal, anal, oral) has occurred between a male participant and a pregnant partner(s) without the use of a condom during and at least for, 70 days after study product administration, the information should be reported to the Sponsor or designee, even if the male participant has undergone a successful vasectomy.

In order for Sponsor or designee to collect any pregnancy surveillance information from the female partner, the female partner(s) must sign an informed consent form for disclosure of this information. Information on the pregnancy will be collected on the Pregnancy Surveillance Form.

9.2.6 Laboratory Test Result Abnormalities

The following laboratory test result abnormalities should be captured on the nonserious AE CRF page or SAE Report Form electronic, as appropriate. Paper forms are only intended as a back-up option when the electronic system is not functioning.

- Any laboratory test result that is clinically significant or meets the definition of an SAE
- Any laboratory test result abnormality that required the participant to have study treatment discontinued or interrupted
- Any laboratory test result abnormality that required the participant to receive specific corrective therapy

It is expected that wherever possible, the clinical rather than laboratory term would be used by the reporting investigator (eg, anemia versus low hemoglobin value).

9.2.7 Potential Drug Induced Liver Injury (DILI)

Specific criteria for identifying potential DILI have not been identified for this protocol. Standard medical practice in identifying and monitoring hepatic issues should be followed.

9.2.8 Other Safety Considerations

Any significant worsening noted during interim or final physical examinations, electrocardiogram, x-ray filming, any other potential safety assessment required or not required by protocol should also be recorded as a nonserious or serious AE, as appropriate, and reported accordingly.

9.3 Overdose

An overdose is defined as the accidental or intentional administration of any dose of a product that is considered both excessive and medically important. All occurrences of overdose must be reported as an SAE (see [Section 9.2.4](#) for reporting details).

9.4 Safety

Planned time points for all safety assessments are listed in the Schedule of Activities [Section 2](#).

9.4.1 New infections

Any new infections that develop during the 60 day study period will be captured as an AE. Type, site and source of culture will be documented in the study record.

9.4.2 Physical Examinations

Refer to Schedule of Activities Section 2.

9.4.3 Chest Imaging

Radiological assessment of symptomatic patients with COVID-19 has been reported to reveal parenchymal abnormalities, regardless of the method used, whether chest x-ray (CXR), computerized tomography (CT) or high resolution computerized tomography (HRCT).⁵⁴ These include bilateral involvement and multilobar ground-glass opacification.³¹ Clinical improvement is also associated with improvement by radiographic assessments.

Because of the restrictions active during the pandemic, the protocol cannot require specific imaging be performed after hospitalization. At screening, it is understood that similar restrictions may be present at study sites, but screening with radiographic chest imaging is considered appropriate due to its utility in identifying other relevant chest disease. Some form of chest imaging (CXR, CT, or HRCT) will be required at screening as part of the inclusion criteria and will also be considered part of TB screening. The reports for this imaging and any additional chest imaging of the lungs performed during the 60 day study period, will be included in the study record.

9.4.4 Vital Signs

Vital signs (VS) will be useful for assessing the clinical progress of study participants. Since VS are captured at varying frequency during hospitalization and not all values will be of reporting utility, the study record will only capture daily values of most interest. For each day (ie, 24 hour

period, midnight to midnight) the participant is hospitalized, vital signs will be extracted from the hospital record and captured in the study record. [REDACTED]

Refer to Schedule of Activities [Section 2](#).

9.4.5 Tuberculosis Screening

Screening for active or latent tuberculosis is routinely performed in abatacept trials. Screening is based on medical history, symptoms, physical exam, CXR and specific testing, either a tuberculin skin test or interferon gamma release assay [(IGRA) eg., T-spot®, QuantiFERON®] approved for local use. Abatacept has not been studied in patients with a positive tuberculosis screen, and the safety of ORENCIA in individuals with latent tuberculosis infection is unknown. Due to the severity of COVID-19, the usual delay to complete TB screening is not feasible and the risk, especially in low risk populations, is low. A tuberculin skin test or IGRA should be performed at screening but randomization does not need to await results if all other aspects of the TB screening, including CXR, are not suggestive of infection. If testing reveals a positive result, medical advice should be obtained to determine whether therapy is warranted.

[figure not shown]
If a tuberculin skin test is performed, it should be interpreted according to the applicable local Health Authority and/or Medical Society guidelines. Documentation of the test results should be recorded in the study record.

9.4.6 Clinical Safety Laboratory Assessments

- Investigators must document their review of each laboratory safety report.

A local laboratory will perform the analyses and will provide reference ranges for these tests. All lab results will be available in an unblinded fashion to hospital clinical staff caring for the participant.

The study will rely on routine safety labs performed as part of routine hospital care. When available, the hematology and chemistry labs listed below will be included in the study record.

Screening for active viral hepatitis B or C is routine in abatacept studies and will be performed in this study, although in a different fashion. Hepatitis B reactivation has been seen in patients treated with abatacept but only in the setting of continuous use, and is a labeled warning. Reactivation of hepatitis C is not a labeled warning. Speed of screening and treatment precludes the feasibility of completing assessment during the screening period and are not warranted. Screening antibodies test will be performed but results will not be needed prior to randomization. If positive results are

noted, confirmatory nucleic acid reflex testing should be ordered and if positive monitor as appropriate.

Table 9.4.6-1: Clinical Safety Laboratory Assessments

Hematology	
Hemoglobin	
Hematocrit	
Total leukocyte count, including differential	
Platelet count	
Chemistry	
Aspartate aminotransferase (AST)	Sodium
Alanine aminotransferase (ALT)	Potassium
Total bilirubin	Chloride
Direct bilirubin	Calcium
Alkaline phosphatase	Phosphorus
Creatinine	Creatinine kinase
Blood urea nitrogen (BUN)	
Uric acid	
Glucose	
Total protein	
Albumin	
Serology	
Hepatitis B surface antigen, hepatitis B core antibody. If either are positive, reflex to hepatitis B DNA testing	
Hepatitis C antibody. If positive reflex to HCV RNA testing	
Other Analyses	
Pregnancy test (WOCBP only: screening)	

9.5 Pharmacokinetics and Immunogenicity Assessments

9.5.1 Pharmacokinetic Assessments

Pharmacokinetic (PK) parameters are not evaluated in this study. [REDACTED]

9.5.2 Immunogenicity Assessments

9.5.2.1 Immunogenicity: Blood Collection

Blood samples for determination of antibodies to abatacept and time-matched PK samples will be from residual volume [REDACTED] on Days 1, 28/ET and 60. For logistical reasons, blood samples will only be obtained for participants who are hospitalized. Sample collection for subjects after hospital discharge will not occur. Samples will be assayed for the presence of abatacept specific antibodies.

9.5.2.2 Immunogenicity: Sample Analysis

[figure not shown]
Anti-abatacept (BMS-188667) Antibody A validated, sensitive, electrochemiluminescence assay (ECL) method will be used to analyze anti-abatacept antibodies in serum. Samples that are confirmed positive for antibodies specific to the CTLA-4 region of abatacept and have abatacept serum concentrations of $\leq 1 \mu\text{g/mL}$ will be further analyzed with a validated, in vitro, cell-based bioassay to determine whether the sera contained abatacept neutralizing activity.

[figure not shown]
9.6 Pharmacodynamics

[figure not shown]
Pharmacodynamic parameters are not evaluated in this study. [REDACTED]

9.7 Pharmacogenomics

Not applicable.

9.9 Health Economics OR Medical Resource Utilization and Health Economics

Not applicable.

9.10 Study Materials

For participants who are discharged from the hospital prior to Day 60, will be provided with the following supplies and document:

- Diary Cards to record body temperature, blood pressure, heart rate, oxygenation, activity level, oxygen use, and symptoms
- Digital thermometer
- Oximeter
- Digital blood pressure monitor
- Subject Alert Card

10 STATISTICAL CONSIDERATIONS

10.1 Sample Size Determination

A 25% estimated rate of progression under placebo plus standard of care to one of the elements of the primary endpoint (mechanical ventilation or death) of hospitalized COVID-19 untreated patients (in particular patients without targeted therapy) was derived from available literature^{1,2,55,56,57,58} and anecdotal feedback. Rates of progression in these reports ranged from 8% to 32%. All reports are from China and include hospitalized patients that had respiratory symptoms. There are different definitions of progression in these reports but most are based on ICU and/or death.

A two group continuity corrected χ^2 test with a 0.150 one-sided significance level will have 80% power to detect the difference between a proportion of 10% abatacept treated participants and a proportion of 25% participants in the placebo group with a primary endpoint event (odds ratio of .33, ie, odds of progression under abatacept versus placebo) when the sample sizes are 86 and 43, respectively (a total sample size of 129). This computation was made using nQuery Advisor version 7. The target sample size for this study is approximately 129 randomized participants.

10.2 Populations for Analyses

For purposes of analysis, the following populations are defined:

Population	Description
Enrolled	All participants who sign informed consent
Intent-to-treat (ITT) Population	All randomized participants, also those randomized and never treated. This population will be used for all efficacy analysis. Analyses using the ITT analysis population will group the participants according to the treatment group to which they are randomized.

Population	Description
Per-protocol (PP) Analysis Population	The PP Population includes all randomized participants excluding the participants with relevant protocol deviations. Relevant protocol deviations are those that may potentially impact the primary endpoint. The relevant protocol deviation criteria will be defined in the statistical analysis plan. If more than 10% of subjects in either treatment group have relevant protocol deviations, the PP Analysis Population will be used for a sensitivity analysis of the primary endpoint.
As-treated Analysis Population	This population includes all randomized participants except those randomized who are not treated. Analyses using the as-treated analysis population will group the participants according to the treatment they received: abatacept or placebo. All safety analyses will use the As-treated Analysis Population.

10.3 Statistical Analyses

To avoid missing data, the data obtained after hospital discharge will be considered for inclusion in all analyses. A description of the participant population will be included in the clinical study report, including subgroups of age, gender and race. Demography and baseline disease characteristics will be presented by randomized treatment group and overall for the ITT population. Continuous variables such as age and weight will be summarized using means, standard deviations, median and ranges. Categorical variables such as gender and race, and ordinal scale score will be summarized using frequencies and proportions.

10.3.1 Efficacy Analyses

Statistical analysis methods for efficacy analyses are provided in Table 10.3.1-1. The primary efficacy endpoint will be formally tested for difference between the treatment groups. Nominal p-values for treatment comparison will be provided for selected secondary endpoints.

Table 10.3.1-1: Efficacy Statistical Analyses

Endpoint	Statistical Analysis Methods
Primary Efficacy Endpoint	The comparison between treatment groups of the proportion of participants with primary endpoint event (mechanical ventilation or death) prior to or on Day 28 will be performed using the Cochran-Mantel-Haenszel (CMH) Chi-Square test, stratified by the randomization stratification factors age group (< 60, ≥ 60) and remdesivir use as well as baseline severity. Baseline severity will be defined by the Clinical Status scale at randomization. A one-sided significance level of 0.15 will be used to assess statistical superiority of abatacept over placebo. The ITT population will be used. Randomized

Table 10.3.1-1: Efficacy Statistical Analyses

[figure not shown]
Endpoint	Statistical Analysis Methods
	
participants with no primary endpoint assessment due to withdrawal of consent or for other reasons will be imputed as treatment failures (ie. progressors). The OR along with its 2-sided 70% CI and 95% CI, as well as the absolute treatment difference in proportions with its 95% will be presented. The construction of CIs for absolute differences in proportions between treatment groups will be based on minimum risk weights⁵⁹ to account for randomization stratification factors and baseline severity.
 
A supplemental analysis of the primary endpoint comparison between the treatment groups will be based on logistic regression with age as a continuous covariate and factors for baseline severity and remdesivir stratification in the model. The nominal p-value for the Chi-square test based on this model will be presented.
 
The primary endpoint is a composite endpoint. The number and percentage of participants progressing to each of the components will be presented by treatment group.
 
The proportion and 95% CI of participants with mechanical ventilation or who died prior to or on Day 28 within treatment group as well as the difference in proportions between the treatment groups and its 95% CI will also be presented by site, age-subgroup (< 60, ≥ 60), remdesivir use (stratification factor), gender, and baseline severity.
 
Kaplan-Meier estimates for the time from randomization to progression to the primary endpoint will be presented. The p-value for the treatment comparison based on the stratified log-rank test, stratified by age-group and remdesivir use, will be presented as a sensitivity analysis of the primary endpoint.

Secondary Binary Endpoints:
	
Proportions and 95% CIs for the binary efficacy endpoints will be presented by treatment group. CIs for proportions within treatment groups will be based on normal approximation. Difference in proportions and 95% CI will be presented, as well as the nominal p-value derived from the CMH Chi-square test stratified by baseline severity and the randomization stratification factors. The construction of CIs for differences in proportions between treatment groups will be based on minimum risk weights to account for randomization stratification factors and baseline severity. A missing response value due to withdrawal of consent or for other reasons will be imputed as a non-responder or progressing.

Table 10.3.1-1: Efficacy Statistical Analyses

Endpoint	Statistical Analysis Methods
Secondary Endpoint: Change from baseline in Ordinal 8-point Outcome Scale	The nominal p-value will be presented for the comparison between treatment groups of the proportion of participants with change from baseline to Day 28 by 1, 2, 3, or 4 categories of worsening, no worsening, or 1, 2, 3, or 4 categories of improvement based on the CMH Row Mean Scores statistic stratified by the randomization stratification factors age-group and remdesivir and baseline severity. Further analyses based on changes in the ordinal 8-point outcome scale will be detailed in the SAP.

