The comparison between treatment groups of the proportion of participants with primary endpoint event (mechanical ventilation or death) prior to or on Day 28 will be performed using the Cochran-Mantel-Haenszel (CMH) Chi-Square test, stratified by the randomization stratification factors age group (<60, \geq 60) and remdesivir use as well as baseline severity. Baseline severity will be defined by the Clinical Status scale at randomization. A one-sided significance level of 0.15 will be used to assess statistical superiority of abatacept over placebo. The population of all randomized participants will be used. Randomized participants with no primary endpoint assessment due to withdrawal of consent or for other reasons will be imputed as treatment failures (ie. progressors). The OR along with its 2-sided 70% CI and 95% CI, as well as the absolute treatment difference in proportions with its 95% CI will be presented. The construction of CIs for absolute differences in proportions between treatment groups will be based on minimum risk weights to account for randomization stratification factors and baseline severity.

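### Minimum risk weights over eight sparse strata make the 95% interval for the primary risk difference too narrow, with about 86–90% coverage under ordinary stratum variances

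*Protocol*

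**What the plan says.** Protocol section 10.3.1, Table 10.3.1-1, reports the primary absolute difference with a 95% CI and fixes how it is built: "The construction of CIs for absolute differences in proportions between treatment groups will be based on minimum risk" weights. The row for secondary binary endpoints repeats the method: "CIs for differences in proportions between treatment groups will be based on minimum risk weights to account for randomization stratification factors and baseline severity". The synopsis gives the same rule for the primary difference: the interval "will be based on minimum risk weights to account for randomization stratification factors and baseline severity".

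The factors are age group (<60, ≥60), remdesivir use (yes, no) and baseline severity, defined by the Clinical Status scale at randomization. Section 9.1.1.2 states that "all study subjects will be in category 3 or 4", so severity has two levels.

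Section 10.1 sets the size: "when the sample sizes are 86 and 43, respectively (a total sample size of 129"), for a "proportion of 10% abatacept treated participants and a proportion of 25% participants in the placebo group". Section 7.2 blocks the randomization within age group by remdesivir use only; severity is not a randomization factor. The formal test is the stratified CMH test at one-sided 0.15.

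**The concern.** Minimum risk weights are calculated from the observed stratum differences and their estimated variances. That works when each stratum holds enough events to estimate its variance. Here each arm of a stratum is expected to hold about one. A stratum that shows few or no events by chance looks precise and gains weight, and the interval formula then treats the weights as fixed constants.

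At stake is the trial's main statement of effect size. Section 5.1 describes a signal-detection study, and section 5.4 says a positive signal should speed a larger one. The absolute difference and its interval will inform that step, and the same construction applies to every secondary binary endpoint.

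**Working it through.** **Inputs from the protocol.** Rates 25% (placebo) and 10% (abatacept); 43 + 86 participants; 2:1 allocation; 2 × 2 × 2 = 8 strata.

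**Inputs assumed, because the protocol gives none.** Stratum shares, prognostic strength and block size (6).

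**The plan's own figure.** The protocol states no coverage beyond the nominal 95%, so the figure to reproduce is the sample size. With z = 1.0364 (one-sided 0.15), z = 0.8416 (80% power) and pooled rate (0.25 + 2 × 0.10)/3 = 0.15:
- Uncorrected placebo n = [1.0364·√(1.5 × 0.15 × 0.85) + 0.8416·√(0.1875 + 0.045)]² / 0.15² = 32.8.
- Continuity-corrected n = (32.8/4)·[1 + √(1 + 6/(32.8 × 2 × 0.15))]² = 42.2, so 43 placebo, 86 abatacept and 129 in total. This agrees with section 10.1; power at 43/86 is 80.6%.

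**Sparsity.** Equal strata hold 86/8 = 10.75 and 43/8 = 5.4 participants, with 10.75 × 0.10 = 1.1 and 5.4 × 0.25 = 1.3 expected events. With 11 and 5 participants, the abatacept arm has no event with probability 0.9¹¹ = 0.31 and the placebo arm with probability 0.75⁵ = 0.24. At least one arm is event-free in 1 − 0.69 × 0.76 = 48% of such strata. The estimated variance is then too small even when it is not zero.

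**Interval as simulated.** In stratum i, d is the difference, V = p₁(1−p₁)/n₁ + p₀(1−p₀)/n₀, and f is the share of the sample. The weights minimise Σw²V + (Σwd − Σfd)² subject to Σw = 1. The CI is Σwd ± 1.96·√(Σw²V).

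**Results at 25% v 10%**, 5,000 trials per row, age ≥60 at 50%. Prognostic means odds ratios of 2 (age) and 3 (severity). The first coverage column adds half an event only where a stratum variance is zero.

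| Remdesivir / state 3 share, risks | Coverage (mean width) | Coverage in trials with no zero-variance stratum and no empty arm | Coverage, every variance smoothed |
|---|---|---|---|
| 50% / 50%, homogeneous | 87.2% (0.247) | 88.0% (2,288 trials) | 93.7% |
| 50% / 50%, prognostic | 88.0% (0.241) | 87.7% (1,114) | 93.5% |
| 70% / 30%, homogeneous | 87.6% (0.254) | 88.5% (598) | 92.8% |
| 70% / 30%, prognostic | 85.6% (0.234) | 84.8% (737) | 91.9% |

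Separate simulations with other shares (remdesivir 50–80%, state 3 20–50%) gave about 86–90%. Two more uneven mixes reached at most 92%.

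**Continuity term.** (3/16)/Σ[n₁n₀/(n₁+n₀)] = 0.1875/(8 × 10.75 × 5.375/16.125) = 0.1875/28.7 = 0.0065 on each side. It lifts coverage over all trials to about 88–91%, and to at most 93% in any mix tried.

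**Other event rates.** The protocol notes: "Rates of progression in these reports ranged from 8% to 32"%. With zero variances patched as in the first coverage column, assumed rates of 32% v 13% gave 86.0–87.8% and 15% v 6% gave 87.0–90.5%. With 25% in both arms coverage was 85.5–87.5%.

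**Why the narrow width is not a real gain.** With homogeneous risks, stratifying cannot improve precision. The unstratified standard error is √(0.09/86 + 0.1875/43) = 0.0735, a 95% width of 3.92 × 0.0735 = 0.288. The minimum risk interval averages 0.247. A half-width of 0.1235 around an estimate with standard error 0.0735 covers only about 91% (z = 1.68), before any allowance for noise in the weights.

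**Number of strata.** Equal shares, homogeneous risks: about 87% with eight strata, 91.1% with four, 93.3% with two.

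**Comparator.** Mantel-Haenszel with Sato variance, same eight strata: about 93.5–94.7%, mean width 0.28–0.29.

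**The case against.** The strongest reply is that the protocol fixes the weights but not the stratum variance estimator, a continuity correction or the handling of sparse strata. These could properly sit in the SAP, which is not shown, or in the cited methods paper. That stands in part. Smoothing every stratum variance gives about 92–95%, adding half an event only where an arm shows 0% or 100% gives 91–94%, and adding it throughout, including in the point estimate, gives 95.5–97.3%. So minimum risk weights do not under-cover under every implementation, and silence on zero cells is no fault in itself. What remains is that the usual reading of the stated method falls well short in this design, including in trials with no zero cell to repair.

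A reader might also infer more than the documents support:
- **That the interval cannot be computed in many trials.** A zero-variance stratum, seen in over half of simulated trials at the design rates, does not stop the minimisation. Only an empty arm leaves a stratum difference inestimable, and its frequency (1–69%) depends wholly on the assumed shares.
- **That the trial's conclusion is at risk.** Success is judged by the CMH test, so type I error and power do not depend on this interval.
- **That the errors favour abatacept.** Misses are lopsided the other way: about 7–10% of intervals lie wholly on the side that understates benefit and 3–5% on the other. Mantel-Haenszel misses lean the same way (4.0–4.4% v 1.8–2.0%), so the lopsidedness is not peculiar to this method.
- **That rare secondary outcomes fare worse by a known amount.** The protocol gives no rates for them, so no figure is offered.

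**Conclusion.** The point holds as a fault in a reported interval, not in the test. Under ordinary binomial stratum variances, the nominal 95% CI for the primary difference covers about 86–90% at the design rates, or two to three times the stated 5% error (10–14% misses). The cause is weights estimated from about one event per arm per stratum, since coverage recovers as strata are merged and stays low in trials that need no patch. The figures rest on assumed stratum shares, prognostic effects and block size; under-coverage with ordinary variances appeared in every mix tried. They do not apply if the SAP smooths all stratum variances. The secondary binary endpoints share the method, but the shortfall there is not quantified. This should be corrected before analysis, but it does not threaten the primary decision.

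**What to change.** In Table 10.3.1-1 (primary and secondary binary endpoints) and in the synopsis, replace minimum risk weights with a Mantel-Haenszel risk difference and Sato variance, keeping age group, remdesivir use and baseline severity as the factors. A stratified Miettinen-Nurminen score interval is an alternative; it was not simulated here. Mantel-Haenszel weights are proportional to n₁n₀/(n₁+n₀), so a stratum with an empty arm gets weight zero without a special rule, and the estimate matches the CMH test.

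The cost is one sentence in each place, with standard software. Against ordinary variances the reported interval is about 10–25% wider (mean width 0.28–0.29 instead of about 0.23–0.26). That extra width reflects uncertainty that is already there.
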